6.1.1 SAFETY LEAD-IN

Safety Lead-In

During the safety lead-in portion of the study, 6 evaluable patients will be enrolled regardless of HR status, to ensure safety of combination radiation and olaparib in gastric/GEJ adenocarcinoma. Patients will be enrolled in a staggered fashion with 10 days minimum between each patient enrolled. The goal of the safety evaluation for the combination is to determine if there are any increased or unexpected toxicities due to combination of agents that would not be expected with either agent alone. Patients in the safety lead-in portion will be included in total planned enrollment.

DLTs:

The DLT evaluation period will be defined as the period from the first dose of combination radiation and olaparib to Cycle 2 Day 21.

A dose-limiting toxicity (DLT) is defined as a drug-related (or at least possibly related) clinically significant adverse event or abnormal laboratory value assessed as unrelated to disease progression, intercurrent illness, or concomitant medications and meeting CTCAE Grade 3 or 4.

If there are no dose limited toxicities, as defined above, we will proceed with the remaining portion of the trial. If $>2/6$ patients experience a DLT attributable to the investigational agents, we will not proceed with the rest of the study.

Once determined that the combination of radiation and olaparib is safe, an additional 20 patients will be enrolled with a planned total enrollment of 13 patients each in the HR deficient and proficient cohorts, respectively. Based on the estimate that 35% of gastric and GEJ cancers will exhibit HR deficiency, we anticipate that the HR proficient cohort will accrue more rapidly than the HR deficient cohort.

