8.3.3 CLASSIFICATION OF AN ADVERSE EVENT

8.3.3.1 SEVERITY OF EVENT

For AEs not included in the protocol-defined grading system, the following guidelines will be used to describe severity.

The adverse event severity grading scale for the NCI CTCAE (v5.0) will be used for assessing adverse event severity. The following table will be used for assessing severity for adverse events that are not specifically listed in the NCI CTCAE (v5.0).

V5.0 CTCAE Grading	
Grade 1	Mild; asymptomatic or mild symptoms; clinical or diagnostic observations only; intervention not indicated.
Grade 2	Moderate; minimal, local or noninvasive intervention indicated; limiting age-appropriate instrumental ADL.
Grade 3	Severe or medically significant but not immediately life-threatening; hospitalization or prolongation of hospitalization indicated; disabling; limiting self-care ADL.
Grade 4	Life threatening consequences; urgent intervention indicated.
Grade 5	Death related to AE

NCI CTCAE □ National Cancer Institute Common Terminology Criteria for Adverse Events. Note: Based on the most recent version of NCI CTCAE (v5.0), which can be found at:

http://ctep.cancer.gov/protocolDevelopment/electronic_applications/ctc.htm

Instrumental activities of daily living refer to preparing meals, shopping for groceries or clothes, using the telephone, managing money, etc.

Examples of self-care activities of daily living include bathing, dressing and undressing, feeding oneself, using the toilet, and taking medications, as performed by patients who are not bedridden.

If an event is assessed as a "significant medical event," it must be reported as a serious adverse event.

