In the event the Safety Portal is experiencing technical difficulties, and the AE information cannot be uploaded, or the acknowledgement was not received, the AE information should be faxed to the Merck GPV [contact], or toll-free [contact]. If fax confirmation is not received within one (1) business day, Principal Investigator/Institution will contact Merck to determine if the original report needs to be re-sent. It should be noted that the Safety Portal should only be used for individual adverse event reporting. Principal Investigator/Institution will maintain a record of the confirmation.

The investigator must record all serious adverse events and report to DSMC and IRB according to timetable for reporting specified in section 10.1.5. Per institutional policy, all serious adverse

events occurring at UCCC/UCHealth will be entered into OnCore according to timetable for reporting specified in section 10.1.5.

The study clinician will complete an SAE Form within the following timelines:

- All deaths and immediately life-threatening events, whether related or unrelated, will be recorded on the SAE Form and submitted to the Merck within 2 working days.
- Other SAEs, regardless of relationship, will be submitted to the Sponsor-Investigator within 24 hours of site awareness and within 2 days to Merck via fax number listed.

For the time period beginning when the consent form is signed until treatment allocation/randomization, any serious adverse event, or follow up to a serious adverse event, including death due to any cause that occurs to any participant must be reported within 24 hours to the Sponsor-Investigator and within 2 working days to Merck Global Safety if it causes the participant to be excluded from the trial, or is the result of a protocol-specified intervention, including but not limited to washout or discontinuation of usual therapy, diet, placebo treatment or a procedure.

For the time period beginning at treatment allocation/randomization through 90 days following cessation of treatment, or 30 days following cessation of treatment if the participant initiates new anticancer therapy, whichever is earlier, any serious adverse event, or follow up to a serious adverse event, including death due to any cause whether or not related to the Merck product, must be reported within 24 hours to the Sponsor-Investigator and within 2 working days to Merck Global Safety.

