10.1.2 STUDY DISCONTINUATION AND CLOSURE

Early trial termination will be the result of the criteria specified below:

1. Quality or quantity of data recording is inaccurate or incomplete
2. Poor adherence to protocol and regulatory requirements
3. Incidence or severity of adverse drug reaction in this or other studies indicates a potential health hazard to participants
4. Plans to modify or discontinue the development of the study drug

In the event of Merck decision to no longer supply study drug, ample notification will be provided so that appropriate adjustments to participant treatment can be made.

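### The lead-in DLT definition stops at CTCAE Grade 4, so a treatment-related death with no recorded Grade 3-4 phase is not counted toward the more-than-2-of-6 stop

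*Combined protocol and SAP*

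**What the plan says.** Section 6.1.1 plans a lead-in in which "6 evaluable patients will be enrolled regardless of HR status". DLTs are collected from the first dose of radiation plus olaparib to Cycle 2 Day 21. A DLT is an adverse event or abnormal laboratory value that is clinically significant, at least possibly drug-related, and "assessed as unrelated to disease progression, intercurrent illness, or concomitant medications and meeting CTCAE Grade 3 or 4".

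Two decision rules rest on that definition:

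- Go: "If there are no dose limited toxicities, as defined above, we will proceed with the remaining portion of the trial".
- Stop: if more than 2 of the 6 "patients experience a DLT attributable to the investigational agents, we will not proceed with the rest of the study".

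The section then says that 20 more patients are enrolled after the radiation and olaparib combination has been judged safe.

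The severity table in section 8.3.3.1 has five grades. Grade 4 covers life-threatening consequences that need urgent intervention. Grade 5 is "Death related to AE".

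**The concern.** The more-than-2-of-6 rule is the only trial-level safety stop in the documents that has a number attached, and its definition leaves out the most severe grade. Both rules inherit the gap, because the go rule refers back to the definition and the stop rule counts DLTs.

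A related death first graded as 5, for example a sudden death or a death between visits, would be missing from the count. Visits become three-weekly from Cycle 2, while the DLT window runs to Cycle 2 Day 21, so such a death is possible. At stake is whether the written count can understate toxicity when expansion is decided. Anyone who counted the death would be departing from the written definition during a safety decision.

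**Working it through.** **Setting the sections side by side.** Section 6.1.1 names Grades 3 and 4. Section 8.3.3.1 separates Grade 4 from Grade 5. No other section defines a DLT, adds Grade 5 to it, or sets a lead-in stop for a related death. Appendix 5, on haematological toxicity, uses open-ended wording (grade 3 and anything worse), which suggests that the closed range in 6.1.1 is a drafting slip.

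**Direct count, no assumptions.** The stop needs 3 or more of 6.

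| Lead-in outcome | Score as written | Score with Grade 5 counted |
|---|---|---|
| 2 patients with a Grade 3-4 DLT, plus 1 related death with no recorded Grade 3-4 phase | 2/6, no stop | 3/6, stop |
| 1 such death, no other DLT | 0/6, go condition met | 1/6, go condition not met, no stop |
| 1 related death with a recorded qualifying Grade 3-4 phase | 1/6 | 1/6 |

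**Effect on the stopping probability.** The plan states no operating characteristic for the lead-in, so there is no figure of its own to reproduce.

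Inputs:
- n = 6 and a stop at 3 or more, from section 6.1.1.
- q, the per-patient probability of a qualifying Grade 3-4 DLT (assumed).
- d, the per-patient probability of a related death in the window with no such event recorded (assumed).

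Patients are taken as independent. A patient is counted with probability p = q as written, and p = q + d once Grade 5 counts.

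P(stop) = 1 − (1−p)^6 − 6p(1−p)^5 − 15p²(1−p)^4

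With q = 0.20:
- As written, p = 0.20: 1 − 0.2621 − 0.3932 − 0.2458 = 0.0989
- d = 0.01, p = 0.21: 1 − 0.2431 − 0.3877 − 0.2577 = 0.1115
- d = 0.02, p = 0.22: 1 − 0.2252 − 0.3811 − 0.2687 = 0.1250
- d = 0.05, p = 0.25: 1 − 0.1780 − 0.3560 − 0.2966 = 0.1694

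| q | d | P(stop) as written | P(stop) with Grade 5 | Change |
|---|---|---|---|---|
| 10% | 2% | 0.016 | 0.026 | +0.010 |
| 10% | 5% | 0.016 | 0.047 | +0.031 |
| 20% | 1% | 0.099 | 0.112 | +0.013 |
| 20% | 2% | 0.099 | 0.125 | +0.026 |
| 20% | 5% | 0.099 | 0.169 | +0.071 |
| 30% | 2% | 0.256 | 0.294 | +0.038 |

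A much higher death rate would be needed for a large effect: with q = 20% and d = 10%, P(stop) goes from 0.099 to 0.256.

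**The case against.** The strongest case on the other side is that the gap is narrow and well backed up. Most of this stands.

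- Sections 8.3.1 and 8.3.4 require changes in an event's severity to be documented. A fatal toxicity that passed through a recorded, related Grade 3 or 4 phase therefore already counts. What is left is a related death with no such phase on record.
- The count does not decide expansion alone. Section 6.1.1 also requires the combination to be judged safe, and gives the lead-in the wider aim of detecting increased or unexpected toxicity.
- Section 8.3.6 requires that any serious event, "including death due to any cause whether or not related to the Merck product, must be reported within 24 hours to the Sponsor-Investigator".
- Section 10.1.2 says that "Early trial termination will be the result of the criteria specified below", and one criterion is "Incidence or severity of adverse drug reaction in this or other studies indicates a potential health hazard to participants". Section 7.1 gives the Sponsor-Investigator similar discretion.
- Section 10.1.5 adds review by the data and safety monitoring committee.

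A reader might infer that a related death would pass unnoticed, or that the trial would be bound to enroll 20 more patients after one. The documents do not support that: several routes lead to review or termination, and an investigator would be unlikely to ignore a related death. A reader might also infer that the plan leaves out every fatal toxicity, which the severity-documentation rule contradicts.

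The backstops do not dispose of the point, however. None has a numerical threshold, and none puts the death into the DLT count.

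**Conclusion.** The point holds as a fault in a stated rule: under the literal text, a related death in the DLT window with no recorded qualifying Grade 3-4 phase is scored as no DLT. This follows from the wording of sections 6.1.1 and 8.3.3.1 and needs no assumption.

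The numerical size does rest on assumed rates. For death rates of 1% to 5% and a 20% Grade 3-4 DLT rate, P(stop) rises by 0.013 to 0.071. A single such death would not trigger the stop even if counted. Counting it would only mean that the lead-in no longer meets the explicit no-DLT condition for going on. The omission is probably unintended and is unlikely to change the trial's course, but it is worth correcting because the rule leaves out the gravest outcome and the correction costs almost nothing.

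**What to change.** In section 6.1.1, change the grade criterion to CTCAE Grade 3 or higher (including Grade 5). Keep all existing qualifiers: clinically significant, drug-related or at least possibly so, and unrelated to disease progression, intercurrent illness or concomitant medications. Deaths from progression or other unrelated causes would still not count.

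The cost is a few words, with no added visits, procedures or data, and a slightly higher chance of stopping if related deaths occur.

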6.1.2 DOSING AND ADMINISTRATION

The treatment to be used in this trial is outlined below:

Drug	Dose/Potency	Dose Frequency	Route of Administration	Regimen/Treatment Period	Use
Pembrolizumab	200 mg	Q3W	IV infusion	Day 1 of each 3 week cycle (excluding Cycle 1)	Experimental
Olaparib*	200mg PO BID	daily	PO	Daily during Radiation D1-21	Experimental
Olaparib*	300mg PO BID	daily	PO	Daily Post-Radiation	Experimental
SBRT	25Gy in 5 fractions	daily M-F	N/A	5 days starting Day 1	Experimental

*During radiation portion, Olaparib dose will be 200mg PO BID. When combined with pembrolizumab, Olaparib dose will be 300mg PO BID.

Trial treatment should begin on the day of treatment (Combination SBRT and Olaparib)

6.1.3 TIMING OF DOSE ADMINISTRATION

6.1.3.1 OLAPARIB

Trial treatment with olaparib should be administered starting on Day 1 of a 21-day cycle. Olaparib tablets will be packed in high-density polyethylene (HDPE) bottles with child-resistant closures. Each dosing container will contain sufficient medication for at least 21 days plus overage. Olaparib will be dispensed to patients on Day 1 and every 21 days thereafter until the patient completes the study, withdraws from the study, or closure of the study. Study treatment is available as a green film-coated tablet containing 100mg or 150mg of olaparib. Patients will be administered olaparib orally twice daily at 200 mg BID concurrently with radiation and 300mg continuously when combined with pembrolizumab. Olaparib tablets should be taken at the same time each day, approximately 12 hours apart with one glass of water. The olaparib tablets should be swallowed whole and not chewed, crushed, dissolved or divided. Olaparib tablets can be

taken with or without food. Trial treatment may be administered up to 7 days before or after the scheduled Day 1 of each cycle (after Cycle 1) due to administrative reasons.

If vomiting occurs shortly after the olaparib tablets are swallowed, the dose should only be replaced if all the intact tablets can be seen and counted. Should any patient enrolled on the study miss a scheduled dose for whatever reason (e.g., because of forgetting to take the tablets or vomiting), the patient will be allowed to take the scheduled dose up to a maximum of 2 hours after that scheduled dose time. If greater than 2 hours after the scheduled dose time, the missed dose is not to be taken and the patient should take their allotted dose at the next scheduled time.

6.1.3.2 PEMBROLIZUMAB

Pembrolizumab 200 mg will be administered as a 30 minute IV infusion every 3 weeks starting with Cycle 2. Sites should make every effort to target infusion timing to be as close to 30 minutes as possible. However, given the variability of infusion pumps from site to site, a window of -5 minutes and +10 minutes is permitted (i.e., infusion time is 30 minutes: -5 min/+10 min).

The Pharmacy Manual provided by Merck contains specific instructions for the preparation of the pembrolizumab infusion fluid and administration of infusion solution.

All trial treatments will be administered on an outpatient basis.

6.2 PREPARATION/HANDLING/STORAGE/ACCOUNTABILITY

6.2.1 ACQUISITION AND ACCOUNTABILITY

The investigator shall take responsibility for and shall take all steps to maintain appropriate records and ensure appropriate supply, storage, handling, distribution and usage of investigational product in accordance with the protocol and any applicable laws and regulations.

Pembrolizumab will be provided by Merck as summarized under 6.2.2.

Olaparib will be provided by Astrazeneca as summarized under 6.2.2. However, shipments will be handled by Merck.

6.2.2 FORMULATION, APPEARANCE, PACKAGING, AND LABELING

Product Name & Potency	Dosage Form
Pembrolizumab 100 mg/ 4mL	Solution for Injection
Olaparib 200mg and 300mg*	Oral tablet

*Separate doses for different treatment periods. Please refer to Table 6.1.2 for more information.

Supplies will be labeled in accordance with regulatory requirements.

This trial is open-label; therefore, the participant, the trial site personnel, the Sponsor-Investigator and/or designee are not blinded to treatment. Drug identity (name, strength) is included in the label text; random code/disclosure envelopes or lists are not provided.

6.2.3 PRODUCT STORAGE AND STABILITY

Clinical supplies must be stored in a secure, limited-access location under the storage conditions specified on the label.

Receipt and dispensing of trial medication must be recorded by an authorized person at the trial site.

Clinical supplies may not be used for any purpose other than that stated in the protocol.

6.2.4 PREPARATION

The Pharmacy Manual contains specific instructions for the preparation of the pembrolizumab infusion fluid and administration of infusion solution.

6.3 STUDY INTERVENTION COMPLIANCE

Since pembrolizumab is given intravenously, and patients must be present at the treatment machine for all radiotherapy, compliance will be confirmed by documentation of pembrolizumab administered as per medical oncology, and radiotherapy treatments documented in the record and verify system as per standard of care.

Drug diaries will be collected at each cycle to confirm Olaparib compliance. Additionally, patients should bring any bottles dispensed for the previous cycle with them to each clinic visit so that treatment compliance can be assessed.

6.4 PROHIBITED THERAPY

6.4.1 PEMBROLIZUMAB

Participants are prohibited from receiving the following therapies during the Screening and Treatment Phase (including retreatment for post-complete response relapse) of this trial:

Antineoplastic systemic chemotherapy or biological therapy

- Immunotherapy not specified in this protocol
- Chemotherapy not specified in this protocol
- Investigational agents other than pembrolizumab or olaparib
- Live vaccines within 30 days prior to the first dose of study treatment, while participating in the study, and for 30 days after the last dose of study intervention. Examples of live vaccines include, but are not limited to, the following: measles, mumps, rubella, varicella/zoster, yellow fever, rabies, BCG, and typhoid vaccine. Seasonal influenza vaccines for injection are generally killed virus vaccines and are allowed; however, intranasal influenza vaccines (eg, FluMist®) are live attenuated vaccines and are not allowed.
- Vaccines for SARS CoV-2 will be permitted
- Systemic glucocorticoids for any purpose other than to modulate symptoms from an event of clinical interest of suspected immunologic etiology. The use of physiologic doses of glucocorticoids is allowed as long as the dose is stable (meaning no increase or on tapering dose) for at least 4 weeks prior to initiating protocol therapy. Other uses may be approved after consultation with the Sponsor-Investigator.

Participants who, in the assessment by the investigator, require the use of any of the aforementioned treatments for clinical management should be removed from the study. All treatments that the Investigator considers necessary for a participant's welfare may be administered at the discretion of the Investigator in keeping with the community standards of medical care.

Medications or vaccinations specifically prohibited in the exclusion criteria are not allowed during the ongoing study. If there is a clinical indication for any medication or vaccination specifically prohibited during the study, discontinuation from study therapy or vaccination may be required. The final decision on any supportive therapy or vaccination rests with the investigator and/or the participant's primary physician. However, the decision to continue the participant on study treatment requires the mutual agreement of the investigator, the Sponsor and the participant.

There are no prohibited therapies during the Post-Treatment Follow-up Phase. If a new therapy is started by participants in the post-treatment follow-up phase they will only be followed for survival.

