^o Drug diaries will be collected and reviewed at the end of each cycle for Olaparib compliance. Additionally, patients should bring any bottles dispensed for the previous cycle with them to each clinic visit (starting at Day 1 cycle 2) for compliance.

^p The simulation planning scan needs to be completed prior to treatment start date. A radiation oncology assessment will occur at least once during the SBRT course as per standard of care. At 2 weeks post-SBRT, a radiation oncology nurse will call patient to assess for any further toxicities. See section 4.3 for additional radiation details.

^q Only Concomitant Medications related to the treatment of AE or SAE, and other medical conditions deemed necessary by the PI will be recorded.

^r For patients who come off treatment for reasons other than progression, follow up scans will be recorded every 12 weeks. Participants who experience confirmed disease progression or start a new anticancer therapy, will move into the Survival Follow-Up Phase and should be contacted by telephone every 12 weeks to assess for survival status until death, withdrawal of consent, or the end of the trial, whichever occurs first. Patients will be followed for 5 years for survival

^s EOT scans are only required if a scan has not been performed within 8 weeks prior to the EOT visit

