6.5 CONCOMITANT THERAPY

Medications or vaccinations specifically prohibited in the exclusion criteria are not allowed during the ongoing trial. If there is a clinical indication for one of these or other medications or vaccinations specifically prohibited during the trial, discontinuation from trial therapy or vaccination may be required. The final decision on any supportive therapy or vaccination rests with the investigator and/or the participants' primary physician.

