7.2 PARTICIPANT DISCONTINUATION/WITHDRAWAL FROM STUDY

Participants are free to withdraw from participation in the study at any time upon request.

In addition, the investigator has the right to withdraw a patient from the study at any time should any untoward effect occur. In addition, a participant may be discontinued from study treatment by the investigator or the Sponsor if study treatment is inappropriate, the trial plan is violated, or for administrative and/or other safety reasons. Specific details regarding procedures to be performed at study treatment discontinuation are provided in Section 8.1.4.1.

A participant must be discontinued from study treatment but continue to be monitored in the study and moved to survival follow-up for any of the following reasons:

- The participant or participant's legally acceptable representative requests to discontinue study treatment
- Confirmed radiographic disease progression outlined in Section 8.1.2.6
- Any progression or recurrence of any malignancy, or any occurrence of another malignancy that requires active treatment

Note: Participants with basal cell carcinoma of the skin, squamous cell carcinoma of the skin, or carcinoma in situ (excluding carcinoma in situ of the bladder) who have undergone potentially curative resection do not have to discontinue study intervention.

- Unacceptable adverse experiences as described in Appendix 5 and Appendix 6.
- The participant has a medical condition or personal circumstance which, in the opinion of the treating investigator and/or sponsor, placed the participant at unnecessary risk from continued administration of study treatment.
- Sponsor-Investigator determines it is in the best interest of the patient
- Patient non-compliance with the study treatment or procedure as determined by the treating investigator
- The participant has a confirmed positive serum pregnancy test
- Recurrent Grade 2 pneumonitis
- Discontinuation of treatment may be considered for participants who have attained a confirmed complete response (CR) and have been treated for at least 8 cycles (at least 24 weeks), receiving 2 cycles of the combination including 2 doses of pembrolizumab and at least 80% of the planned doses of olaparib and pembrolizumab beyond the date when the initial CR was declared. These participants may be eligible for second course treatment described in Appendix 7.
- Administrative reasons

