8.1.1.3.2 SUBSEQUENT ANTI-CANCER THERAPY STATUS

The investigator or qualified designee will review all new anti-neoplastic therapy initiated after the last dose of trial treatment. If a participant initiates a new anti-cancer therapy within 30 days after the last dose of trial treatment, the 30 day Safety Follow-up visit must occur before the first dose of the new therapy. Once new anti-cancer therapy has been initiated the participant will move into survival follow-up.

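### Section 6.4.1 takes a treated participant who needs a prohibited therapy off the study, while neighbouring rules stop treatment at most and keep the patient in follow-up (minor wording conflict)

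*Combined protocol and SAP*

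**What the plan says.** Section 6.4.1 lists therapies that are barred during screening and treatment: other antineoplastic, immune or investigational agents, live vaccines, and systemic glucocorticoids outside stated exceptions. The steroid exceptions are treatment of suspected immune events and stable physiologic doses, with an approval route for the rest: "Other uses may be approved after consultation with the Sponsor-Investigator". Participants who, in the investigator's assessment, "require the use of any of the aforementioned treatments for clinical management should be removed from the study".

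The next paragraph of 6.4.1 is milder. If a prohibited medication or vaccination is indicated, "discontinuation from study therapy or vaccination may be required", and the participant may stay on study treatment if investigator, Sponsor and participant agree. Section 6.5 uses the same form: "discontinuation from trial therapy or vaccination may be required". Section 6.4.1 closes by saying that nothing is barred once a patient is in post-treatment follow-up.

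The follow-up rules are general:
- Section 1.3, footnote r: "For patients who come off treatment for reasons other than progression, follow up scans will be recorded every 12 weeks".
- Section 7.2, lead-in to the list of reasons: "A participant must be discontinued from study treatment but continue to be monitored in the study". One listed reason is "Sponsor-Investigator determines it is in the best interest of the patient". Prohibited therapy is not named.
- Section 8.1.1.3.2: "Once new anti-cancer therapy has been initiated the participant will move into survival follow-up".
- Section 8.1.2.6.2 asks for imaging every 12 weeks in patients who stop without progression, and 8.1.4.3 places those who stop for another reason in the Follow-Up Phase.

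**The concern.** The protocol separates leaving treatment from leaving the study, and 7.2 is built on that distinction. The 6.4.1 sentence uses the stronger of the two terms and covers patients already on treatment, not only those in screening, where removal is normal. One event can therefore be handled in three ways: off study, off treatment with follow-up, or still on treatment by agreement. No sentence says which rule governs.

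If a site follows the words literally, imaging and survival data stop for a treated patient because of a clinical need that may be related to prognosis. OS, PFS and DoR would then be censored early, possibly informatively, and a response seen once might never be confirmed.

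**Working it through.** **The plan's figure, for reference.** Section 9.2 gives 26 patients for ORR 0.25 against 0.45, one-sided alpha 0.1, power 0.8. With the exact binomial, P(X ≥ 10 | 26, 0.25) = 0.091 and P(X ≥ 10 | 26, 0.45) = 0.806. A cut-off of 9 gives alpha 0.180, so the rule is 10 or more responses. The design reproduces, and this point disputes no part of it.

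**Step 1. Which prohibited therapies are exposed?**

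| Therapy needed on treatment | Other text that decides the case | Exposed to the 6.4.1 wording? |
|---|---|---|
| New anticancer therapy | 8.1.1.3.2 and Section 1.3 footnotes k and r: survival follow-up | No, already answered |
| Steroid for a suspected immune event, or stable physiologic dose | Exempt in 6.4.1 | No |
| Other steroid use, approved | Approval route in 6.4.1 | No |
| Other steroid use, not approved | None specific | Yes |
| Live vaccine | None specific; continuation only by agreement | Yes |

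The last two rows are the exposed group. The documents give no frequency for either.

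**Step 2. What does the scan schedule imply for one such patient?** Inputs are from 8.1.2.6.1 and 8.1.2.6.2, in days from allocation.
- First scan: 63 ± 7 = day 56 to 70. The schedule table in Section 1.3 shows ± 3 days instead: day 60 to 66.
- Confirmation of a response at least 4 weeks (28 days) later: no earlier than day 56 + 28 = 84 to 70 + 28 = 98. With ± 3 days: day 88 to 94.
- The end-of-treatment scan is not mandatory if imaging exists from the previous 8 weeks (56 days).

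Suppose a response is first seen on the first scan and the patient comes off for an unapproved steroid course in the following weeks. The end-of-treatment scan is then not required. Under literal removal no later scan is due, and the response stays unconfirmed. Under 8.1.2.6.2 the next scan comes at 12 weeks, or 84 days, which exceeds the 28 days needed for confirmation. Section 8.1.4.3 prints 42 days beside 12 weeks, and that interval would also be long enough.

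A patient removed before the first scan would have at most an end-of-treatment scan and no later confirmation.

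**Step 3. Which analyses are touched?** Section 9.4.3 plans no formal tests for secondary endpoints, so OS, PFS and DoR are descriptive. Section 9.3 keeps every eligible treated patient in the analyses, so a removed patient is not dropped from the ORR denominator. The possible effect on ORR is limited to whether a response is seen and confirmed.

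**The case against.** The strongest reply is that the protocol, read as a whole, already settles follow-up.
- Section 7.2 lets the investigator or Sponsor stop study treatment when it is inappropriate or the trial plan is violated. That fits a patient who needs a barred drug, and the action is to stop treatment. The best-interest reason in its list can reach the same patient.
- Section 8.1.2.6.2 lists what ends imaging: new anticancer treatment, progression, pregnancy, death, withdrawal of consent and end of study. A steroid course or a vaccine is not there. Section 8.1.4.3 is equally general.
- The last paragraph of 6.4.1 lifts all prohibitions in post-treatment follow-up, which suggests that such a patient leaves treatment and enters follow-up. Its next sentence limits those who start a new therapy to survival follow-up. I read that as new anticancer therapy, in line with footnote k.

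Much of this stands. The treatment-only reading is well supported and probably intended. A reader might infer from Section 7.3 that removal means no further data of any kind, survival included. The documents do not support that inference: 7.3 says so for patients lost to follow-up, and 6.4.1 carries no such statement.

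What remains is that 6.4.1 is the sentence written for this event, it uses a different and stronger term, and nothing says that it means treatment only. Approval by the Sponsor-Investigator covers steroids but not vaccines, and it does not say what follows when approval is not given.

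**Conclusion.** A minor internal conflict, worth correcting because the sentence states a rule that a site could apply literally. The exposed group is treated patients who need a live vaccine or a steroid course that is neither exempt nor approved, and it is probably small. The possible harm is early, perhaps informative, censoring of descriptive OS, PFS and DoR, and in some patients an unconfirmed response. Frequency and direction are unknown. The conclusion assumes that at least one site would read the sentence literally; if all read it as treatment only, nothing is lost.

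Two stronger readings should not be drawn. A reader might infer a loss of power for the primary ORR test by counting removed patients as non-responders. No document gives a removal rate, so no such figure has a basis. A reader might also infer that each removal forfeits five years of survival calls under 8.1.4.3. Those calls end at death or at the end of the trial; the synopsis gives a total study length of 4 years; and Section 2.1 puts median first-line survival at 9 to 11 months, while these patients are previously treated.

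**What to change.** In 6.4.1, for participants who have started treatment, replace the removal instruction with: *discontinued from study treatment (unless, for a non-anticancer therapy, continuation is agreed as stated in the next paragraph) and followed per 8.1.2.6.2 and 8.1.4.3: imaging every 12 weeks until progression or new anticancer therapy, then survival follow-up.* Removal during screening can stay.

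Two safeguards:
- Keep the absolute bar on concurrent anticancer therapy in 6.4.2. The option to continue must apply only to non-anticancer therapies; a general qualifier such as *if required* would loosen that bar.
- If prohibited therapy is added to the reasons in 7.2, state that imaging continues for patients without progression. The lead-in there moves patients to survival follow-up, which alone would drop their scans.

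The cost is amendment wording. The scans and telephone contacts are already in the protocol, and sample size, cut-off and alpha are unchanged.
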